5.3 ANALYSIS OF PERIOD 2 OUTCOMES

There are no pre-specified hypotheses associated with the safety or performance endpoints. The Period 2 outcomes will be summarized using descriptive statistics. Pvalues may be calculated for relevant comparisons but will be considered exploratory.

All available data from Period 2 will be included in analysis. Participants who have agreed to participate in Period 2, but provide minimal data, may be excluded from analysis at the discretion of the sponsor.

At the commencement of Period 2, in the event of logistic and/or site scheduling/approval or device delivery challenges occurring for some participants of the Intervention group preventing a continuous use, a switch-back to previous device is accepted for a maximum of 6 months, before activating therapy with the CE-marked commercial Omnipod 5 System with the clinical study site support. Similarly, such a delay in transitioning participants in the Control group to the Omnipod 5 System is also acceptable. Any data collected during that "study pause" will not be included in analysis.

6 ANALYSIS OF SAFETY

All adverse events reported during the study will be reviewed and adequately reported to comply with applicable regulations. All reportable AEs will be assessed by the investigator who will determine whether the event is related to the study procedures or related to the study device and whether the event meets any of the criteria for seriousness. The event will be considered serious if the event meets at least one criterion for seriousness.

6.1 MEDICAL MONITOR

A Medical Monitor will be responsible for individual and timely review of adverse events, including serious adverse events (SAEs) and adverse device events. The Medical Monitor will conduct adjudication of any events of DKA or severe hypoglycemia or any additional events as requested by the Sponsor. The specified events will be adjudicated to determine event relatedness to the study procedures and/or the devices (participant's own insulin pump, study CGM and Omnipod 5), and whether an adverse event is unanticipated. The adjudication decision of the Medical Monitor will be used for the final classification of events, including relatedness to the study procedures and/or the devices, for the determination of safety endpoints and for all regulatory reports, product labeling, and publications or presentations.

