9.5 Hypoglycemic Events

Hypoglycemia is only reportable as an adverse event when one of the following criteria is met:

- Severe Hypoglycemia: The event required assistance of another person due to altered consciousness, and required another person to actively administer carbohydrate, glucagon, or other resuscitative actions²¹. This means that the participant was impaired cognitively to the point that he/she was unable to treat himself/herself, was unable to verbalize his/her needs, was incoherent, disoriented, and/or combative, or experienced seizure or loss of consciousness. These episodes may be associated with sufficient neuroglycopenia to induce seizure or loss of consciousness. If plasma

glucose measurements are not available during such an event, neurological recovery attributable to the restoration of plasma glucose to normal is considered sufficient evidence that the event was induced by a low plasma glucose concentration.

- Hypoglycemia resulting in an SAE that may not otherwise meet the definition of Severe Hypoglycemia defined above.

When a hypoglycemic event meets the above reporting requirements, an Adverse Event Form should be completed. A severe hypoglycemia event should be considered a serious adverse event and follow the SAE reporting requirements.

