9.12 Safety Oversight

The Medical Monitor will review all adverse events and adverse device events that are reported during the study. SAEs will typically be reviewed within 24-hours of reporting. Upon receipt of the SAE Report Form, the Medical Monitor will determine whether the event is unanticipated based on the investigator brochure (IB).

A listing of all AEs will be reviewed periodically by the Medical Monitor as part of routine safety signal detection.

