10.3 Safety Signal Detection

Selected data from this study will be reviewed periodically to detect as early as possible any safety concern(s) related to the device so that Investigators, clinical study participants, regulatory authorities, and IRBs/IECs will be informed appropriately and as early as possible.

The Medical Monitor will conduct adjudication of any events of DKA or severe hypoglycemia or any additional events as requested by the Sponsor. The specified events will be adjudicated to determine:

- event relatedness to the study procedures and/or the devices (participant's own insulin pump, study CGM and Omnipod 5)
- whether an adverse event is unanticipated

The adjudication decision of the Medical Monitor will be used for the final classification of events, including relatedness to the study procedures and/or the devices, for the determination of safety endpoints and for all regulatory reports, product labeling, and publications or presentations.

Detailed roles and responsibilities of the Study Physician and Medical Monitor are described in the SMP.

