7.3 CONTROL OF SYSTEMATIC BIAS

Several measures are incorporated into the study design to help minimize study bias as follows:

- This is a randomized, multi-center study to help ensure that investigator or site or participant enrollment bias is minimized. Selection of participants will be made from the Investigator's usual participant load. Consecutively eligible participants should be enrolled into the study.
- 2) This document specifies appropriate statistical methodology to ensure that bias is minimized.
- 3) The effectiveness measures will be based on the direct output from the device or are analyzed at a NGSP certified central laboratory, ensuring objective reporting.
- 4) A Medical Monitor will adjudicate all SAEs and device-related adverse events to ensure consistency across all evets; the Medical Monitor's assessment of adverse events will be used for regulatory reports, product labeling, and publications or presentation.

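### SAP 6.1 and SAP 7.3 give different scopes for Medical Monitor adjudication; if 7.3 relies on the site's rating, non-serious events can be re-rated only downwards

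*SAP*

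**What the plan says.** **Scope, first statement.** SAP 6.1: "The Medical Monitor will conduct adjudication of any events of DKA or severe hypoglycemia or any additional events as requested by the Sponsor". Protocol 10.3 has the same scope. It introduces the questions to be decided with "The specified events will be adjudicated to determine" and lists two: relatedness to procedures or devices, and whether the event is unanticipated.

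**Scope, second statement.** SAP 7.3, item 4 of the list of bias controls: "A Medical Monitor will adjudicate all SAEs and device-related adverse events to ensure consistency across all evets".

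**Who rates first.** SAP 6: "All reportable AEs will be assessed by the investigator who will determine whether the event is related to the study procedures". The same sentence extends this to relatedness to the study device.

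**What adjudication does.** SAP 6.1: "The adjudication decision of the Medical Monitor will be used for the final classification of events". This expressly includes relatedness and reaches safety endpoints, regulatory reports, labeling and publications. SAP 7.3 gives the Medical Monitor's assessment a similar role. SAP 6.2 reduces the rating to related or not, counting possibly related as related, and SAP 6.5 tabulates events by that relationship.

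**Seriousness.** Protocol 9.5: "A severe hypoglycemia event should be considered a serious adverse event". Protocol 9.6 treats DKA in the same way.

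**Review, as distinct from adjudication.** Protocol 9.12: "The Medical Monitor will review all adverse events and adverse device events that are reported during the study".

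**The concern.** Both scope statements are in the SAP, so the rule that the SAP overrides the protocol (SAP 1, Protocol 12.7) does not settle which applies. Two teams working in good faith from different sections would send different events to the Medical Monitor and could produce different tables of related events.

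Each version also has its own weakness. Under 6.1, everything beyond DKA and severe hypoglycemia depends on a Sponsor request for which no criteria are given. Treatment is evident from the device in use, the investigator rates relatedness first, and Sponsor representatives see CGM and Omnipod 5 data during the trial (Protocol 12.2, SAP 7.10). Under 7.3, selection of non-serious events appears to depend on the same rating that adjudication is meant to check. At stake are the relatedness breakdown of adverse events and any labeling or publication statement drawn from it.

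**Working it through.** The plan gives no figure to reproduce, so the check sets the two scopes side by side. Reportable events fall into three classes (DKA or severe hypoglycemia; other SAE; non-serious AE), each crossed with the site's rating. For 7.3 the table assumes that device-related means the investigator's rating; the section does not say whose rating it means.

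| Event class | Site's device rating | SAP 6.1 and Protocol 10.3 | SAP 7.3 |
|---|---|---|---|
| DKA or severe hypoglycemia | related | adjudicated | adjudicated |
| DKA or severe hypoglycemia | unrelated | adjudicated | adjudicated |
| Other SAE | related | only if Sponsor asks | adjudicated |
| Other SAE | unrelated | only if Sponsor asks | adjudicated |
| Non-serious AE | related | only if Sponsor asks | adjudicated |
| Non-serious AE | unrelated | only if Sponsor asks | no route |

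**How far the scopes differ.** The two agree in 2 of 6 cells and differ in 4 of 6. In three of the four, adjudication is mandatory under 7.3 and optional under 6.1. In the fourth, it is optional under 6.1 and has no route under 7.3.

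**Direction of re-rating.** Let R be the number of events in a class that sites rate related, r the number of these re-rated unrelated, and u the number of site-unrelated events re-rated related. The final related count is

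R − r + u.

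- DKA or severe hypoglycemia: r and u can both be above zero under either scope.
- Other SAEs: both can be above zero under 7.3. Under 6.1 both depend on Sponsor requests.
- Non-serious AEs: under 7.3, u = 0 by construction, so the count is R − r and cannot exceed R. Under 6.1 both terms depend on Sponsor requests.

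The one-way effect is therefore built into one of three classes under 7.3 and into none under 6.1.

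**A concrete case.** Prolonged hyperglycemia with raised ketones is reportable under Protocol 9.6, which says that hyperglycemia short of DKA is generally not serious. Protocol 7.4.1 and 9.2 say that an occluded or displaced cannula should be suspected, which is a device mechanism. The relatedness call is still open to judgment: a note in Protocol 9.3 brings user error into the definition of an adverse device effect, and a later paragraph there generally leaves out events due solely to user error. If the site decides unrelated, 7.3 never tests that decision.

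**A bound.** Under Protocol 9.4, a non-serious event not judged a device effect is reportable only through another listed route, such as device discontinuation or impact on glucose control, effect on study procedures, an emergency department visit, or a glycemic event. Reportable hypoglycemia under Protocol 9.5 is either severe or already an SAE. The untested non-serious glycemic events are therefore the hyperglycemic and ketotic ones.

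**Illustration only.** The documents give no event counts. If R were 20 and 20% to 30% were re-rated down (both assumed), r would be 20 × 0.20 = 4 to 20 × 0.30 = 6, leaving 14 to 16, with nothing able to enter from the other side under 7.3.

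**The case against.** The strongest defence is that the two sections can be reconciled in practice. A standing Sponsor request covering all SAEs and device-related events would make 6.1 operate like 7.3, and Protocol 10.3 places the Medical Monitor's detailed duties in the Safety Management Plan, which was not available here. That plan may settle the scope. It is a fair limit on this point, but neither SAP section refers to it for scope, and a standing request would leave the selection of non-serious events tied to the device-related rating.

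A second defence is that the Medical Monitor reviews every adverse event, so a mis-rated one would be seen. That is true, but the documents do not say that review alone changes a rating; SAP 6.1 gives that force to the adjudication decision. A third is that 7.3 does not say whose rating makes an event device-related. This stands, and it is why the one-way conclusion is conditional.

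A reader might also infer more than the documents support:

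- *That adjudication in general can only reduce the related count.* It cannot be said for SAEs, because 7.3 takes all of them whatever their rating.
- *That severe hypoglycemia and DKA counts depend on which section is followed.* Both sections require adjudication of every such event.
- *That re-rating could move the total across the five-event threshold for testing in SAP 5.2.5.* The threshold counts events, not related events, and the listed adjudication questions do not include whether an event meets its definition.
- *That near-miss events are never adjudicated.* A glycemic event that is an SAE without meeting the DKA or severe hypoglycemia definition is covered by 7.3, and others can be added under 6.1.
- *That the rule must favour Omnipod 5 in the comparison of arms.* Section 7.3 does not limit device-related to one device, so the direction of any between-arm effect is not determined.

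**Conclusion.** The inconsistency is real and should be resolved: the sections treat four of six combinations of event class and site rating differently, and the result feeds the final relatedness classification. Two weaknesses follow. Under 6.1, adjudication beyond DKA and severe hypoglycemia rests on Sponsor requests without stated criteria; any one-way effect there would come from how requests are made, not from the rule. Under 7.3, the related count for non-serious events can fall but not rise, provided device-related means the investigator's rating.

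The consequence is confined to relatedness reporting. The primary and secondary efficacy analyses are untouched, and SAEs can be re-rated in either direction wherever they are adjudicated. The numerical effect cannot be estimated from the documents. A related but separate gap is that neither section asks the Medical Monitor to confirm that an event meets the definitions in Protocol 9.5 or 9.6.

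**What to change.** State one scope, in the same words, in SAP 6.1, SAP 7.3 and Protocol 10.3, applied to both arms:

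1. All SAEs, including all severe hypoglycemia and DKA.
2. Non-serious events selected without regard to the site's relatedness rating: all reportable hypoglycemic and hyperglycemic or ketotic events, all events leading to device discontinuation, and all other reportable events of the types 7.3 now covers, whether rated related or not.
3. Sponsor-requested additions only under criteria fixed in advance, with each request documented. Keeping this route is preferable to deleting it, because under 6.1 it is the only stated way for a non-serious event rated unrelated to reach adjudication.

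Add to the adjudication questions whether the Protocol 9.5 or 9.6 definition is met. Keep the Medical Monitor's decision as the final classification, and tabulate the investigator's and the Medical Monitor's relatedness ratings side by side so that movement in each direction is visible. If the Safety Management Plan already contains a scope, align it with this text.

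The cost is wording in three places, one extra table and a little more adjudication work. The Medical Monitor already reviews every reported event, so the added burden should be small. Related-event counts may come out slightly less favourable.

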6.2 RELATIONSHIP TO STUDY DEVICE AND PROCEDURE

The causal relationship to the study procedures and the investigational device for each adverse event will be rated as follows:

- Unrelated: The event is not related to the procedures or the investigational device.
- Possibly Related: The temporal sequence is such that the relationship is not unlikely or there is no contradicting evidence that can reasonably explain the participant's

condition. There is a possibility of any relation between the event and the procedures or the devices.

- Related: The temporal sequence is relevant, or the event abates upon completion of the procedure/ use of devices, or the event cannot be reasonably explained by the participant's condition or comorbidities. The event is related or most likely associated with the procedures or the devices.
- Causal Relationship (for French sites only): The serious event is associated with the investigational device or with procedures beyond reasonable doubt.

For the purposes of dichotomizing the causal relationship in safety summaries, events that are "Related" or "Possibly Related" (or have a "Causal Relationship", French sites only) will be considered related.

6.3 SEVERITY

The severity of the adverse event will be rated based upon the following grades:

- Mild: Usually transient, requires no special treatment, and does not interfere with the participant's daily activities.
- Moderate: Usually causes a low level of inconvenience, discomfort or concern to the participant and may interfere with daily activities but is usually ameliorated by simple therapeutic measures and participant is able to continue in study.
- Severe: Interrupts a participant's usual daily activities, causes severe discomfort, may cause discontinuation of study device, and generally requires systemic drug therapy or other treatment.

6.4 OUTCOME

The outcome of each reportable adverse event will be classified by the investigator as follows:

- Recovered/Resolved: The participant recovered from the AE/SAE without sequelae.
- Recovered/Resolved with Sequelae: The event persisted and had stabilized without further anticipated change in the event status.
- Fatal: A fatal outcome is defined as the SAE that resulted in death. Only the event that was the cause of death should be reported as fatal. AEs/SAEs that were ongoing at the time of death; however, were not the cause of death, will be recorded as "resolved" at the time of death.
- Not Recovered/Not Resolved (Ongoing): An ongoing AE/SAE is defined as the event was ongoing with an undetermined outcome.

• Unknown: An unknown outcome is defined as an inability to access the participant or the participant's records to determine the outcome (for example, a participant that was lost to follow-up).

6.5 ANALYSIS OF ADVERSE EVENTS

Safety summaries and analyses will be based on all participants that are randomized into the study (i.e., modified Intention to Treat analysis set). All adverse events reported over the course of the study will be summarized and tabulated by study phase (standard therapy vs. randomized period), event category, seriousness, severity, and relationship to the study procedures and the investigational device. Except where indicated, a participant reporting the same adverse event more than once will be counted once when calculating the number and percentage of participants with that particular event.

Adverse events leading to death or to discontinuation from the study will be listed separately. A listing of all adverse events will be provided. Adverse events for participants excluded from mITT analysis set will be listed separately.

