7.2.1 Assessment of CGM Usage and Data Criteria

7.2.1.1 Current Dexcom G6 Users (US Sites Only)

Current Dexcom G6 users may be exempt from the standard therapy 14-day period if the following criteria are met:

- Willing to provide 14-days of CGM data from the past 30-days
- Meet the success criteria of 80% CGM use during any consecutive 14-days in the past 30-days
- Must have $\geq 2,016$ CGM values during the 14-days

The site staff will review the device use and data criteria to see if they have met the exemption criteria. If exemption criteria are not met, participants may choose to continue to collect data until they meet the criteria or will be required to participate in the entire 14-day standard therapy period consistent with the requirements for non-G6 users.

If participants meet the criteria, they will be immediately eligible to proceed with Visit 3, in which case Visit 1, Visit 2, and Visit 3 may occur on the same day, commencing the 13-week study.

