9.4 Reportable Adverse Events

Adverse events will be assessed on an ongoing basis throughout the study. Adverse event reporting will begin at the start time of the standard therapy (i.e., insertion of the CGM sensor) and continue until the participant's participation has ended. All adverse events must be followed until resolution, or until the AE has stabilized, or until the study has been completed.

Pre-existing medical conditions or symptoms observed prior to the start time of the standard therapy phase will not be recorded as an AE and should be collected in the participant's medical history. In the event there is a change (i.e., worsening) in the pre-existing medical condition or symptoms after enrollment meeting the criteria of a reportable adverse event, then an AE must be reported.

For this protocol, a reportable adverse event includes any untoward medical occurrence that meets one of the following criteria:

1. An SAE
2. An ADE unless excluded from reporting in Hypoglycemic Events and Hyperglycemic/Ketotic Events sections below
3. An AE not related to a study device issue which leads to temporary or permanent discontinuation of the study devices or the participant's own insulin pump, or creates a clinically significant impact on a participant's glucose control
4. An AE that affects the participant's ability to complete any study procedures
5. An AE for which a visit is made to a hospital emergency department
6. Hypoglycemic Events as defined below
7. Hyperglycemia/Ketotic Events as defined

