11.6.1 ITT (Intention to Treat) Analysis Set

The ITT analysis set includes all participants that are enrolled in the study. All safety analyses will be based on the ITT analysis set.

11.6.2 mITT (modified Intention to Treat) Analysis Set

The modified Intention to Treat (mITT) analysis set is a subset of the ITT analysis set. The mITT analysis set will consist of all participants who have been randomized. The mITT analysis set will be used as the primary analysis for the primary and secondary endpoints and for other clinical outcome data.

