7.2.1 ITT (Intention to Treat) Analysis Set

The ITT analysis set includes all participants that are enrolled in the study.

7.2.2 mITT (modified Intention to Treat) Analysis Set

The modified Intention to Treat (mITT) analysis set is a subset of the ITT analysis set. The mITT analysis set will consist of all participants who have been randomized. The mITT analysis set will be used as the primary analysis for the primary and secondary endpoints, as well as safety analyses, and for other clinical outcome data.

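### The SAP restricts safety tables to randomized participants but still tabulates a phase before randomization, so events in people who leave before randomization reach only the listings, and the protocol names a different safety population

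*SAP*

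**What the plan says.** The two documents name different safety populations.

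- Protocol 11.6.1: "All safety analyses will be based on the ITT analysis set", where "The ITT analysis set includes all participants that are enrolled in the study". Enrollment is the moment the participant starts wearing the study CGM (Protocol 7, SAP 2.6).
- SAP 6.5: "Safety summaries and analyses will be based on all participants that are randomized into the study (i.e., modified Intention to Treat analysis set". SAP 7.2.2 repeats this, assigning the mITT set to the efficacy endpoints "as well as safety analyses, and for other clinical outcome data", and defines the set: "The mITT analysis set will consist of all participants who have been randomized".
- Protocol 12.7 and SAP 1 both give the SAP precedence where the documents differ.

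SAP 6.5 also commits to tabulating every adverse event reported during the study "by study phase (standard therapy vs. randomized period". According to Protocol 9.4, "Adverse event reporting will begin at the start time of the standard therapy", which that section equates with CGM insertion. Events in participants outside the mITT set get a separate listing (SAP 6.5). SAP 6.6 handles device deficiencies in the same manner as adverse events.

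For current Dexcom G6 users at US sites who meet the exemption criteria, Protocol 7.2.1.1 says "they will be immediately eligible to proceed with Visit 3", and adds that Visits 1, 2 and 3 can then fall on one day.

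**The concern.** The population for the standard-therapy table is defined by an event, randomization, that comes after the phase is over. Someone who has a reportable event in those two weeks and leaves can never enter that table. SAP 6.5 thus promises a tabulation of every reported event by phase and, in the same paragraph, names a population on which it cannot be done.

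The denominator raises a second question. Exempt participants with same-day visits are randomized, so they count in the standard-therapy column although they have practically no time in that phase.

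What is at stake is the standard-therapy incidence, for adverse events and for device deficiencies, and agreement between the protocol and the SAP on who is in the safety population.

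**Working it through.** **Inputs.** Protocol 11.5 and SAP 4.1 give 131 completers, 170 randomized, up to 200 enrolled, attrition up to 15% before randomization and up to 22.9% after it. Neither document gives an adverse event rate or a number of exempt participants; values for these below are assumptions.

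**Step 1: the plan's figures.** For a 10-point difference, SD 16.5, two-sided 5% and a 2:1 split of 87 and 44, a two-sample t test has power 0.902, which agrees with the stated 90%. The inflation also reproduces:

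- 131 / (1 − 0.229) = 169.9, rounded up to 170
- 170 / (1 − 0.15) = 200

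**Step 2: people outside the SAP table.** 200 − 170 = 30, and 30/200 = 15%. This is the planned maximum. These people leave both the numerator and the denominator of the standard-therapy incidence.

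**Step 3: effect of the leavers.** Let p be the incidence among the 170 randomized and k the leavers' risk as a multiple of p.

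- Rate under the SAP: p
- All-enrolled rate: (170p + 30kp) / 200
- Share of affected people missing from the table: 30k / (170 + 30k)

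With p = 2.0% (assumed), the randomized contribute 3.4 expected affected people and the leavers 0.6k:

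| k (assumed) | SAP table | All enrolled | Affected people not in table |
|---|---|---|---|
| 0 | 2.0% | 3.4/200 = 1.7% | 0% |
| 1 | 2.0% | 4.0/200 = 2.0% | 15% |
| 2 | 2.0% | 4.6/200 = 2.3% | 26% |
| 3 | 2.0% | 5.2/200 = 2.6% | 35% |
| 5 | 2.0% | 6.4/200 = 3.2% | 47% |

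The SAP figure is too high when k is below 1, equal when k is 1, and too low when k is above 1.

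**Step 4: effect of the exempt participants.** If a fraction f of the denominator spent no time in the phase, x affected people give x/170 in the table and x / [170(1 − f)] among those exposed. The table shows (1 − f) times the rate among the exposed, so this effect can only be downward. For assumed f of 25% or 50% the factor is 0.75 or 0.50. The actual f cannot be derived: the documents do not say how many will be exempt, and same-day visits are permitted, not required. This effect does not come from the choice between ITT and mITT, because the protocol's all-enrolled set contains the same people.

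**Step 5: what does not change.** Leavers have no arm and no randomized-period time, and Omnipod 5 is first dispensed at Visit 3 (Protocol 7.4). The test of severe hypoglycemia and DKA rates counts events in the randomized period only (SAP 5.2.5). For those analyses the mITT set is suitable.

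**The case against.** The strongest reply is that nothing is lost and nothing is ambiguous. The precedence clauses tell the analyst which set to use. SAP 6.5 provides a listing of all adverse events, another for participants outside mITT, and another for events leading to death or discontinuation. SAP 7.8 describes baseline for all enrolled as well as for mITT. A careful reader could rebuild the all-enrolled count. The phase covers usual therapy, lasts about 14 days, has no arms, and is not formally compared with the randomized period.

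Most of that stands, and it limits the weight of the point. It does not remove it. Precedence settles which rule governs, not whether the rule fits a table of a phase before randomization, and the SAP gives no reason for departing from the protocol. A listing does not correct a reported incidence.

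A reader might infer that the standard-therapy rate is biased low overall. The documents do not support that for the leavers. Leaving need not follow an adverse event: randomization also requires meeting the CGM usage and data criteria (Protocol 7.4.1), and leavers with fewer events would make the SAP rate too high. Only the exemption effect has a known direction. A reader might also infer that the randomized-period column gains an unfair comparator. No such comparison is specified, and raw incidences over about 14 and about 90 days would not be comparable on any denominator.

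**Conclusion.** The point holds as a mismatch between the documents and a wrong denominator for one descriptive phase. Following the SAP leaves up to 30 of 200 enrolled participants (15%) out of the standard-therapy incidence, so SAP 6.5 cannot deliver the by-phase tabulation it describes. On an assumed 2.0% among those randomized, the all-enrolled rate lies between 1.7% and 3.2% for leavers at 0 to 5 times that risk; both the 2.0% and the multiples are illustrative. Exempt participants lower the phase incidence further by an unknown factor (1 − f), and would do so under the protocol's set too.

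It would be a mistake to read this as hidden safety data or as a threat to the between-arm safety results. The events are listed, and the randomized-period analyses, sample size and power do not change. The change is worth making because it is cheap, not because a safety conclusion depends on it.

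**What to change.** In SAP 6.5, 6.6 and 7.2.2:

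- Base standard-therapy adverse event and device-deficiency tables on all enrolled participants who entered that phase, excluding exempt participants with no standard-therapy days.
- Keep the mITT set, by arm, for the randomized-period tables.
- State in the SAP how this departs from Protocol 11.6.1 and why. Since the SAP prevails, this reconciles the documents without requiring a protocol amendment for this point alone.

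Reverting to the protocol's all-enrolled set would bring the leavers back but leave the exempt participants in the denominator, so it is only half a remedy.

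The cost is SAP wording and one extra table denominator. SAP 7.8 already calls for summaries of both the enrolled and mITT populations. The standard-therapy rate may look slightly less favourable. One limit remains: the early withdrawal visit is held only for participants who completed Visit 3 (Protocol Table 1, footnote e), so events and deficiencies in earlier leavers can be counted only as far as sites reported them.
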